Appendix D: Protocol Revisions

SAP	Statistical Analysis Plan
TLR	Target Lesion Revascularization
TVR	Target Vessel Revascularization

3. Introduction

This document outlines the detailed statistical methods to be implemented for the data collected within the scope of the Medtronic Durability PAS Study. The purpose of this plan is to provide a framework within which answers to the study objectives can be achieved in a statistically rigorous fashion, without bias or analytical deficiencies. Specifically, this Plan has the following purpose: To prospectively (a priori) outline the types of analyses and presentations of data that will form the basis for conclusions to be reached that will answer the clinical evaluation objectives outlined in the protocol, and to explain in detail how the data will be handled and analyzed, adhering to commonly accepted standards and practices of biostatistical analysis in the medical device industry. Results obtained from the analyses outlined in this document will be the basis of the Final Study Report for the overall Clinical Investigational Plan (CIP).

4. Study Objectives

The purpose of this study is to confirm the safety and effectiveness of primary stenting with the EverFlex™ Self-Expanding Peripheral Stent System (EverFlex stent) when used in subjects with atherosclerotic stenoses, restenoses or occlusions of the native superficial femoral artery or superficial femoral and proximal popliteal arteries through three years post-procedure.

Primary Endpoint: The primary endpoint of the study is composite endpoint defined as freedom from acute death, freedom from 36-month amputation, and freedom from 36-month clinically-driven target lesion revascularization compared to a PTA performance goal.

Secondary Endpoints:

- 1. Freedom from Stent Fracture:** Determined by x-ray at 1, 2 and 3 years using the following classifications:

- Class 0 – No strut fractures
- Class I – Single tine fracture
- Class II – Multiple tine fractures
- Class III – Stent fracture(s) with preserved alignment of the components
- Class IV – Stent fracture(s) with mal-alignment of the components
- Class V – Stent fracture(s) in a trans-axial spiral configuration

AND the following categories:

- Category A – Restenosis \leq 50% at site of fracture
- Category B – Restenosis $>$ 50% at site of fracture
- Category C – Occlusion at site of fracture
- Category D – Unable to determine

- 2. Freedom from acute death, freedom from amputation and freedom from clinically-driven target lesion revascularization at 1 and 2 years:** Defined as the absence of all-cause mortality occurring within 30-days, absence of any major amputation within 12-/24- months and the absence of any clinically-driven repeat invasive procedure, including angioplasty, stenting, endarterectomy, bypass, or thrombolysis, performed to open or increase the lumen diameter inside or within 10 mm of the previously treated lesion due to the return of clinical symptoms within 12-/24-months of the procedure.
- 3. Freedom from 36-month amputation:** Defined as the absence of any major amputation (removal of the target limb or a part of the target limb above the metatarsal line) within 36 months of the procedure.
- 4. Freedom from 36-month clinically-driven target lesion revascularization:** Defined as the absence of any clinically-driven repeat invasive procedure, including angioplasty, stenting, endarterectomy, bypass, or thrombolysis, performed to open or increase the lumen diameter inside or within 10 mm of the previously treated lesion due to the return of clinical symptoms within 36 months of the procedure.
- 5. Freedom from acute death:** Defined as the absence of all-cause mortality occurring within 30-days of the procedure.
- 6. Device Success:** Defined as the ability to deploy the stent as intended at the treatment site.

7. **Improvement in Rutherford Clinical Category at 1 Year:** Defined as an improvement in clinical status indicated by a decrease of one or more in Rutherford Clinical Category compared to baseline.
8. **Improvement in Ankle-Brachial Index at 1 Year:** Defined as an increase in the ankle-brachial index (ABI) compared to baseline in subjects with compressible arteries and baseline ABI < 0.9.
9. **Walking Improvement at 1 Year:** Defined as an increase in Walking Impairment Questionnaire score in subjects who did not have iliac disease treated at the time of the index procedure compared to baseline.
10. **Adverse Event Rate:** Defined as the rate of adverse events that occur during the course of the study; event and subject counts as well as proportions of subjects with events categorized by type will be reported. Note that adverse events are captured at each study assessment. Counts and rates of all-cause mortality will be reported both as part of the overall adverse event profile as above, and separately as a specific outcome.

5. Investigation Plan

DURABILITY PAS is a prospective, multi-center, non-randomized, single arm study with sequential enrollment of all qualified subjects undergoing treatment of atherosclerotic lesions in the native superficial femoral artery or the superficial femoral and proximal popliteal arteries. All eligible subjects who provide informed consent will undergo PTA and stenting using the EverFlex device. Follow-up will take place at pre-discharge, 30 days, 1 year, 2 years and 3 years.

6. Determination of Sample Size

Primary Endpoint and Sample Size Adjustment

The study's primary endpoint has been previously defined. The associated statistical hypothesis is that the resulting event-free rate at 36 months is greater than the Performance Goal (PG), which is adapted from RESILIENT 3-year data on freedom from TLR for PTA subjects.

The null and alternative hypotheses for the primary endpoint are:

$$H_0: \pi_t \leq \pi_{pg}$$

$$H_a: \pi_t > \pi_{pg}$$

where π_t is the event-free rate in subjects treated with an EverFlex device and π_{pg} is the PG of 35%.

Analysis of this endpoint will be carried out by Kaplan-Meier methods. The point estimate of the event-free rate at 36 months (1095 days) from the date of the index procedure will be computed along with its one-sided 97.5% lower confidence bound. If the lower bound is greater than 35%, it will be declared that the PG and the corresponding primary study objective have been met.

Justification of Performance Goal

The structure of the composite endpoint is derived from a 12-month composite endpoint described by VIVA Physicians Inc. (VPI) as part of their development of safety and effectiveness Performance Goals (PG) for the use of bare nitinol stents in the treatment of femoropopliteal lesions.^{1,2} The VPI 12-month

composite was defined as acute death, index limb amputation and target vessel revascularization (TVR) through 12-months. This composite event rate in the studies reviewed was 30.5% at 12 months (Table 1). However, there were no long-term follow-up to 3 years reported.

Table 1: PTA Performance Goals – Safety Data

	Company A (n=29)	Company B (n=24)	Company C (n=63)	Combined (n=116)
12 month Composite (acute death, 12m TVR, 12m amputation)	38.5% (10/26)	33.3% (6/18)	25.5% (13/51)	30.5% (20/95)

Three-year data on freedom from TLR was presented on the PTA arm of the RESILIENT study.³ The reported event-free rate at 3 years among RESILIENT subjects randomized to PTA treatment was 41.8%, a value which is adjusted as follows to account for longer lesions enrolled in DURABILITY II.

The statistical model employed is a Cox regression on the outcome of freedom from TLR applied to DURABILITY II data. Lesion length (in mm) as measured by the core laboratory was the predictor of outcome, resulting in a point estimate of 0.01543 for the logarithm of the hazard ratio, and therefore a hazard ratio of $e^{0.01543}=1.0155$ per mm of lesion length (with longer lesions associated with lower freedom-from-TLR rates).

As the mean lesion length in RESILIENT was 68 mm versus 89 mm in DURABILITY II, the resulting adjusted event-free rate can be obtained using a formula analogous to adjusting with odds ratios:

$$\pi_{pg}/(1-\pi_{pg}) = (0.418/(1-0.418)) * 1.0155^{(89-68)}$$

Solving this equation gives $\pi_{pg} = 0.342$, which is rounded up to give the PG of 35%. Note that this PG is conservative in that it (1) does not attempt to account for any other systematic differences between RESILIENT and DURABILITY II and (2) does not explicitly account for the other elements of the composite endpoint (since these were not presented for RESILIENT), which if included would lower the expected freedom-from-event rate below that seen for TLR alone.

Potential Outcomes

Table 2 summarizes approximate outcomes under potential results for freedom from event, using binomial estimation. Note that the actual analysis will be conducted using time-to-event methods and is subject to currently unknown censoring times, and that therefore the actual success criteria will vary slightly from those noted below.

Table 2: Approximation to Possible Outcomes and Corresponding 97.5% Lower Confidence Bound Primary Endpoint (PG=35%)			
Sample Size	Count of subjects with freedom from event	36-Month Freedom From Event Rate	97.5% lower confidence bound
108	48	44.4%	35.1%
108	49	45.4%	36.0%
108	50	46.3%	36.9%
108	51	47.2%	37.8%

Sample Size and Power

The required sample size for evaluating the primary endpoint can be approximated using the normal method for testing a single proportion (as above, under Kaplan-Meier methods the actual power will vary slightly from this calculation):

$$n = \frac{(\pi_{pg} \times (1 - \pi_{pg})) \times (Z_{1-\alpha} + Z_{1-\beta} \sqrt{\pi_t(1 - \pi_t) / (\pi_{pg}(1 - \pi_{pg}))})^2}{(\pi_t - \pi_{pg})^2}$$

Where,

- Type I error (α) = 0.025 (one-sided)
- Statistical power ($1 - \beta$) = 90%
- Z is the standard normal deviate for $\alpha = 0.025$ and $\beta = 0.10$.
- π_t is estimated freedom-from-event at 36 months
- π_{pg} is the PG

Using this approximation with $\pi_t = 0.55$ (estimated from current DURABILITY II data), $\pi_{pg} = 0.35$ (the *a priori* performance goal), $Z_{1-\alpha} = 1.96$ and $Z_{1-\beta} = 1.28$ gives a sample size of 62. Allowing for approximately 30% of subjects lacking a 3-year follow-up visit, the needed sample size under this approximation for 90% power is a minimum of 89.

An additional sample size requirement is based on the secondary endpoint of freedom from stent fracture at 1 year. In DURABILITY I and DURABILITY II, 1-year stent fracture rates of 8.1% (n=151) and 0.4% (n=287), respectively, were observed. The pooled fracture rate of these two studies is 3.0% (13/438), around which a confidence interval of specified width is desired. The desired precision is 7.2%

(half-width of 3.6%); we therefore find a 95% two-sided normal confidence interval with upper bound $3.0\% + 3.6\% = 6.6\%$, and extract the relevant sample size.

Table 3: Sample Size Freedom from Stent Fracture

Sample Size for Freedom from Stent Fracture			
Sample Size	Count of subjects with event	Event Rate	97.5% upper confidence bound (95% two-sided)
95	3	3.16%	6.67%
96	3	3.13%	6.61%
97	3	3.09%	6.54%
98	3	3.06%	6.47%

From the above table, the required sample size at 1 year is 97 subjects. Considering a 10% rate of attrition, a minimum of 108 subjects are needed, which is larger than the sample size of 89 calculated for the primary endpoint. The enrolled sample size is therefore 108. Please note that multiple stents are allowed in each subject in the study. The stent fracture endpoint will be analyzed on stent level. To be conservative, sample size calculation is performed on subject level. Therefore, more stents than the above assumption may be included in the analysis.

7. Statistical Methods

7.1 Study Subjects

7.1.1 Disposition of Subjects

The number of subjects who are selected, and who have a scheduled follow-up visit will be summarized at each scheduled visit.

7.1.2 Clinical Investigation Plan (CIP) Deviations

Protocol deviations will be reported descriptively by counts of type and listing by site.

7.1.3 Analysis Sets

All study subjects with non-missing values will be included in the primary endpoint analysis and secondary endpoint analysis.

7.2 General Methodology

All statistical analyses will be performed using Statistical Analysis System (SAS) for Windows (version 9.2 or above, SAS Institute Inc. Cary, N.C.) or other widely accepted statistical or graphical software. In general, data for all study subjects combined will be presented. Individual data will be presented in subject listings.

Descriptive statistics will be used to present the data and to summarize the results. Discrete variables will be presented using frequency distributions and cross-tabulations. Continuous variables will be summarized by presenting the number of observations (N), mean, standard deviation, median, minimum, and maximum values.

For adverse event reporting, the primary analysis will be based on subject counts, not event counts. A subject with more than one event will be counted only once toward the event rate based on the total number of subjects with adverse events.

Unless otherwise specified, statistical significance will be declared when $p < 0.05$ for two-sided tests and $p < 0.025$ for one-sided tests such as the primary endpoint.

7.3 Center Pooling

This is a multi-center clinical study, with standardization of subject enrollment, data entry and adverse event reporting. All investigational sites will follow the requirements of a common protocol, data collection procedures and case report forms. To present the data from this clinical study in a summary form, a comparison across all sites will be completed to determine if the generated data could be pooled. The following variables will be completed to assess the appropriateness of pooling data from across all sites:

- Baseline demographics such as age and gender
- Lesion characteristics such as lesion length and percent stenosis

The distributions of the above variables across the sites will be tabulated.

[figure not shown]
7.4 Handling of Missing Data and Dropouts

In general, imputation of missing data will not be performed for all analyses. Subjects who dropped out will be censored at date of last follow-up contact.

7.5 Demographic and Other Baseline Characteristics

All demographic, medical history and clinically relevant baseline variables will be summarized and tabulated. Descriptive statistics will be presented as follows:

- Categorical variables, including binary variables, will be reported by giving the number and percentage of patients in each category.

- Continuous variable will be reported by presenting the number of observations, mean, standard deviation, median, IQR, minimum, and maximum of each variable

7.6 Treatment Characteristics

Device success defined as the ability to deploy the stent as intended at the treatment site will be reported.

7.7 Evaluation of Objectives

Analysis of the primary endpoint will be carried out by Kaplan-Meier methods. The point estimate of the event-free rate at 36 months (1095 days) from the date of the index procedure will be computed along with its one-sided 97.5% lower confidence bound. If the lower bound is greater than 35%, it will be declared that the PG and the corresponding primary study objective have been met.

For secondary endpoints, descriptive statistics will be provided. No formal statistical hypothesis testing will be performed. Categorical variables will be analyzed using frequency tabulation and event rate. For continuous variables, analysis will include mean, median, standard deviation, and ranges. Time-to-event variables including the primary endpoint and the secondary endpoint of freedom from stent fracture will be analyzed using survival analysis and reported at 1 year (365 days), 2 years (730 days) and 3 years (1095 days), with Kaplan-Meier plots provided.

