DURABILITY II enrolled 287 subjects at 44 investigational sites in both the United States and Europe. A total of 303 stents were implanted: single stents in 95% (272/287), and 5.0% (15/287) received multiple stents. The mean age of subjects was 68 years, with 66% male. Co-morbidities include hypertension (88%), hyperlipidemia (86%), and diabetes (43%). The mean lesion length measured by core laboratory was 89.1 mm. The mean normal-to-normal lesion length measured by sites was 109.6 mm. Deployment of the stent at the intended treatment site was achieved in 99.3% of subjects. No major adverse events occurred at 30 days. Primary duplex ultrasound stent patency at 1 year in all subjects including single-stent and multi-stent implants was 67.7%. The primary patency by Kaplan Meier estimate at 1 year was 77.2%. At 2 and 3 years, primary patency was 66.1% and 60.0%, respectively. The mean Rutherford classification fell from 2.8 ± 0.6 (range 2-5) at baseline to 0.6 ± 1.1 (range 0-5) at 1 year. The mean ankle-brachial index rose from 0.65 ± 0.15 (range 0.06-0.89) at baseline to 0.89 ± 0.20 (range 0.25-1.77), 0.88 ± 0.19 (range 0.26, 1.27) and 0.89 ± 0.19 (range 0.31, 1.33) at 1, 2, and 3 years, respectively. The 1-year stent fracture rate was 0.4%; and was 0.9% at 2 and 3 years, respectively.

DURABILITY 200

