The subject is enrolled in the study after he/she has signed the subject informed consent and it has been determined that he/she meets all of the inclusion criteria and none of the exclusion criteria. The point of enrollment is defined as the moment an exchangeable guidewire crosses the lesion and/or re-enters the true vessel lumen distal to the target lesion(s). *Figure 2* provides a flow diagram from the point of subject screening through continuing follow-up visits.

Figure 2: Study Flow Diagram from Subject Screening to Follow-up

Overview of Study Conduct

Table 1 provides an overview of the assessment requirements for the study, and Tables 2-7 provide the specific requirements at each stage of the study.

Assessment Schedule (Timeframe Window)	Baseline (45 days prior, labs 30 days prior)	Procedure	Pre- Discharge	30 Days (25-40 Days)	1 Year (335-395 Days)	2 Years (685-775 Days)	3 Years (1050-1140 Days)
Medical history	Х						
Physical exam	Х						
Clinical status by Rutherford Clinical Category	X			Х	Х		
Ankle-brachial index†	Х			Х	Х	Х	Х
Walking Impairment Questionnaire	Х			Х	Х	Х	Х
Angiogram†		Х					
Laboratory tests‡	Х						
X-ray (fracture assessment) †					Х	Х	Х
Adverse event documentation		Х	Х	Х	Х	Х	Х
Amputation		Х	Х	Х	Х	Х	Х
Death		Х	Х	Х	Х	Х	Х
Clinically Driven Target Lesion Revascularization		Х	Х	Х	X	Х	Х

Table 1: Study Assessment Requirements

[†]If a subject requires a re-intervention of the target vessel, a resting ABI, x-ray evaluation for stent fracture and angiogram are to be performed prior to the procedure. If possible, all non-invasive assessments should be captured for the study, including ABI, and x-ray evaluation, even if the re-intervention and angiogram are declined. [‡]Creatinine and White Blood Cell count

Performance of study assessments at unscheduled follow-up visits should be done as clinically indicated and corresponding data must be submitted to the sponsor.

Baseline Requirements

Baseline data collection requirements are identified in Table 2. Baseline assessment results will be submitted to the sponsor.

Table 2: Baseline Requirements

Baseline Requirements	Timeframe Window
Medical history	
Physical exam	
Clinical status by Rutherford Clinical Category	Within 45 days
Ankle-brachial index	
Walking Impairment Questionnaire	
Laboratory tests (creatinine and white blood cell count)	Within 30 days

Procedure Requirements

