X-rays should be sent out to the core laboratory for evaluation within five business days. The core laboratory will review the x-rays for quality and the presence of stent fracture. The core laboratory will communicate to the investigational site within seven business days after receiving the x-rays if the image quality is inadequate to make an assessment of stent fracture and will also provide guidance on specific measures for the site to take in order to adequately assess for stent fracture. If the image quality of the x-ray is inadequate to make an assessment of stent fracture, the investigational site must request that the subject return for a second series of x-rays.

Study coordinators will be trained on the quality assessment measures used for x-ray acquisition for stent fracture assessment. It is recommended that the study coordinators be present at the time of the x-ray acquisition to provide direction and guidance to the x-ray personnel. Each site must review x-rays for image quality prior to sending to core lab.

Table 6 lists the 1-year follow-up assessment requirements.

1-Year Follow-up Requirements	Follow-up Window
Clinical status by Rutherford Clinical Category	
Ankle-brachial index	
Walking Impairment Questionnaire	1-Year Visit:
X-ray	335-395 Days Post-Procedure
Adverse event documentation	
Primary Endpoint Assessments: Amputation, Death,	
Clinically Driven Target Lesion Revascularization	

 Table 6: 1-Year Follow-up Assessment Requirements

2-Year and 3-Year Follow-Up Requirements

All subjects are required to have follow-up visits at 2 and 3 years. Ankle-brachial index Walking Impairment Questionnaire, and an evaluation for AEs will be completed and documented at each visit. X-ray imaging to identify stent fracture is also required. Refer to the Manual of Operations for the x-ray imaging and transmission requirements.

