If a subject is clinically indicated for a re-intervention of the target vessel, a resting ABI, xray evaluation for stent fracture and angiogram are to be performed and documented prior to the endovascular procedure. If possible, all non-invasive assessments should be captured for the study, including ABI, and x-ray evaluation, even if the re-intervention and angiogram are declined. If the subject does not want to undergo an angiogram, re-intervention, or noninvasive assessments it will not be considered a deviation from the clinical protocol. In the event a subject declines to proceed with an angiogram, re-intervention, or non-invasive testing, the reason will be documented in the subject's medical record.

Termination of Participation

All subjects have the right to terminate themselves from participation at any point during the study. In addition, Principal Investigators also have the ability to terminate subject participation in the study (see page 26, "Subject Withdrawal" for rationale for physician-directed withdrawal). A description of the reason for their termination will be documented. Reasons for termination include: completion of study, subject withdrawal, physician-directed subject withdrawal, lost-to-follow-up, and death.

Loss to Follow-Up

Every attempt must be made to have all subjects complete the follow up visit schedule. A subject will not be considered lost-to-follow-up unless efforts to obtain compliance are unsuccessful. At a minimum, the effort to obtain follow-up information must include three attempts to make contact via telephone and if contact via phone is not successful, then a certified letter from the Principal Investigator must be sent to the subject's last known address. Both telephone and letter contact efforts to obtain follow up must be documented in both the subject's medical records and on the study case report forms (CRFs).

Subject Withdrawal

All study subjects have the right to withdraw their consent at any time during the study. Whenever possible, the site staff should obtain written documentation from the subject that wishes to withdraw his/her consent for future follow-up visits and contact. If the site staff is unable to obtain written documentation, all information regarding the subject's withdrawal must be recorded in the subject's medical record. In addition, the appropriate CRFs must be completed for the subject and clear documentation of the subject's withdrawal be provided to the sponsor.

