In the event of a UADE the investigational site will inform the sponsor and IRB as soon as possible. A written report will be provided to the sponsor within 10 business days after the investigator learns an unanticipated adverse device effect and will be provided to the IRB according to the board's reporting guidelines.

Deaths

Each subject death must be reported to the sponsor. A death must be reported to the sponsor as soon as possible after the site's knowledge of the event. A written report will be provided to the sponsor within 10 business days after the investigator learns of a death and will be provided to the IRB according to the board's reporting guidelines. It is requested that a copy of the death certificate and a copy of the autopsy report, if applicable, be sent to the sponsor when available. Any other source documents related to the death should also be provided to the sponsor. In the event that no source documents are available the PI will be required to submit a letter to the sponsor describing the circumstances of the subject's death.

Core Laboratory Requirements

Angiographic Core Laboratory

An independent Angiographic Core Laboratory will review all scheduled and unscheduled angiographic procedure data. See Angiographic Core Laboratory Procedures in the Manual of Operations.

The Angiographic Core Laboratory is:

[name] Medical Director Beth Israel Deaconess Medical Center Angiographic Core Laboratory [name] [contact] [contact]

X-ray Core Laboratory

An independent x-ray Core Laboratory will review all scheduled and unscheduled x-ray data. See X-ray Core Laboratory Procedures in the Manual of Operations.

The X-ray Core Laboratory is:

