Descriptive statistics will be used to present the data and to summarize the results. Discrete variables will be presented using frequency distributions and cross-tabulations. Continuous variables will be summarized by presenting the number of observations (N), mean, standard deviation, median, minimum, and maximum values.

For adverse event reporting, the primary analysis will be based on subject counts, not event counts. A subject with more than one event will be counted only once toward the event rate based on the total number of subjects with adverse events.

Unless otherwise specified, statistical significance will be declared when p<0.05 for twosided tests and p<0.025 for one-sided tests such as the primary endpoint.

Analysis of Secondary Endpoints

For secondary endpoints, descriptive statistics will be provided. No formal statistical hypothesis testing will be performed. Categorical variables will be analyzed using frequency tabulation and event rate. For continuous variables, analysis will include mean, median, standard deviation, and ranges. Time-to-event variables including the primary endpoint and the secondary endpoint of freedom from stent fracture will be analyzed using survival analysis and reported at 1 year (365 days), 2 years (730 days) and 3 years (1095 days), with Kaplan-Meier plots provided.

Analysis of Ability to Pool Data Across Investigational Sites

This is a multi-center clinical study, with standardization of subject enrollment, data entry and adverse event reporting. All investigational sites will follow the requirements of a common protocol, data collection procedures and forms. To present the data from this clinical study in a summary form, a comparison across all sites will be completed to determine if the generated data could be pooled. The following variables will be completed to assess the appropriateness of pooling data from across all sites:

- Baseline demographics such as age and gender
- Lesion characteristics such as lesion length and percent stenosis

The distributions of the above variables across the sites will be tabulated. To detect site differences, t-tests or Wilcoxon's rank-sum test will be used for continuous variables and Fisher's exact test for categorical variables.

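### Stent fracture is seen only on windowed x-rays but is read from a survival curve at exactly days 365, 730 and 1095, with no rule for dating fractures or for censoring at the last film

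*SAP*

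**What the plan says.** **How fracture is observed.** Both documents define the first secondary endpoint by x-ray at 1, 2 and 3 years (Protocol 4.0, Secondary Endpoints; SAP 4). Protocol Table 1 sets the visit windows: "1 Year (335-395 Days"), days 685 to 775 for year 2, and "3 Years (1050-1140 Days"). Table 6 repeats "335-395 Days Post-Procedure" for the year-1 film. Other films also count. For a target-vessel re-intervention, an x-ray "evaluation for stent fracture and angiogram are to be performed and documented prior" to the procedure (Protocol, Unscheduled Assessments During Follow-up), and "An independent x-ray Core Laboratory will review all scheduled and unscheduled x-ray data" (Protocol, Core Laboratory Requirements). If image quality is inadequate, the subject is asked back for a second series.

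**How it is analysed.** SAP 7.7 names fracture as a time-to-event variable: "freedom from stent fracture will be analyzed using survival analysis and reported at 1 year (365 days"). Protocol 5.0, Analysis of Secondary Endpoints, has the same plan: "reported at 1 year (365 days), 2 years (730 days) and 3 years (1095 days), with Kaplan-Meier plots provided".

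**What the plan says on dating and censoring.** SAP 7.4 censors dropouts at their last follow-up contact and in general does not impute. SAP 7.1.3 includes subjects with non-missing values. The Stent Fracture Adjudication Committee rules on class and category; the protocol does not give it the date. Neither document ties a fracture to the film date, the nominal visit or an interval.

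**What the endpoint is used for.** SAP 6 sizes the study on the 1-year fracture proportion: 97 evaluable subjects, 108 enrolled. SAP 7.7 makes secondary endpoints descriptive, with no hypothesis test.

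**The concern.** A Kaplan-Meier estimate at day 365 counts only events dated on or before day 365. Each reading day is the midpoint of its film window, so about half of the permitted 1-year film days come after the 1-year reading. A fracture first seen on a perfectly compliant film on day 380 would be counted at 1 year or not according to a convention that the plan does not state.

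Censoring raises a second question. For an endpoint visible only on x-ray, last contact is not evidence that a stent is intact. A dropout could be carried as fracture-free up to a contact at which no film was taken.

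At stake is the reported 1-year rate of the first secondary endpoint, which is also the quantity whose precision set enrolment. The sizing used a simple proportion among evaluable subjects. A survival curve read at day 365 estimates the same thing only if films are mapped to visits first.

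**Working it through.** **1. The plan's own figure.** SAP 6 uses the normal upper bound p + 1.96 × √(p(1 − p)/n) with 3 events.

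| n | 3/n | upper bound |
|---|---|---|
| 95 | 3.16% | 6.67% |
| 96 | 3.13% | 6.61% |
| 97 | 3.09% | 6.54% |
| 98 | 3.06% | 6.47% |

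The target is 3.0% + 3.6% = 6.6%, and 97 is the first size in the table to meet it. Then 97/0.90 = 107.8, giving 108. The plan's figures reproduce, and they are for a proportion among 97 evaluable subjects.

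**2. Share of each window after the reading day.** Year 1: days 366 to 395 are 30 of the 61 days from 335 to 395, or 49%. Years 2 and 3: 45 of 91 days, or 49%.

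**3. The design case under film dating.** Assumptions: 3 fractures in 97 stents, one stent per subject, all year-1 films in window, and film days uniform over the window. The documents give no distribution of film days, so uniformity is for illustration only.

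- Chance that at least one of the three is filmed after day 365: 1 − (31/61)³ = 87%.
- Chance that all three are: (30/61)³ = 12%.

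*(a) Intact stents stay at risk past day 365*, for example because they have a later film or contact. The reading is the number filmed by day 365 divided by 97, so it can be 0, 1.03%, 2.06% or 3.09%. Its mean is 3 × (31/61)/97 = 1.6%.

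*(b) Intact stents are censored at their year-1 film.* The risk set shrinks day by day through the window, so each fracture counted weighs more. The expected cumulative hazard to day 365 is approximately (3/97) × (1/61 + 1/60 + … + 1/31) = 0.0309 × 0.701 = 2.2%. Simulation agrees: mean 2.2%, with 95% of runs between 0 and about 4.7%.

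*(c) In-window films assigned to day 365.* All three fractures fall on day 365 with 97 at risk: 3/97 = 3.1%. Nothing is lost.

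**4. Dependence on visit timing.** For 3.0% found, with film dating and intact stents at risk past day 365, the average reading is 1.5% with even timing. It is 2.4% if visits run 10 days early and 0.7% if they run 10 days late (SD 12 days, also assumed).

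**5. Later readings.** The later error depends on how many fractures are new in each year. In DURABILITY II, "The 1-year stent fracture rate was 0.4%; and was 0.9% at 2 and 3 years, respectively". With no new fractures in year 3, the day-1095 reading equals the rate found. With an assumed 3%, 4% and 5% found by years 1, 2 and 3, day 1095 reads 4.7% on average with even timing (4.2% late, 5.6% early).

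**6. Would interval censoring alone restore the proportion?** Using the year-1 films of the design case, a Turnbull estimate at day 365 averages 2.8%, with 95% of runs between 0 and about 5.3%. It reads 0% in 12% of runs and equals 3/97 in only 2%. It is not interchangeable with (c).

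**7. Exact interval for the proportion.** For 3/97 = 3.1%, the Clopper-Pearson 95% interval is 0.6% to 8.8%.

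**The case against.** The strongest reply is that the loss comes from a convention the plan does not adopt. Fracture is defined as determined at 1, 2 and 3 years, Table 1 labels the day 335 to 395 film as the 1-year film, and the windows are centred on the reading days. A programmer could reasonably index films by visit, and then nothing is lost. This stands as far as it goes: a reader might infer that the planned analysis will halve the fracture rate, and the documents do not support that. What remains is that the SAP, whose stated purpose includes explaining in detail how data will be handled, does not make the choice, and ordinary time-to-event programming on film dates gives a different answer.

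A reader might also infer that the sample size or the study's conclusion is in doubt. It is not. The 108 was fixed from a proportion before analysis, and no test rests on this endpoint. At the design rate the average shift under film dating is about 1.5 points, less than half the planned half-width of 3.6. At the DURABILITY II rate of 0.4% it is negligible.

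Other defences carry less weight. The SAP 7.7 sentence on frequency tabulation concerns categorical variables, while the same paragraph lists fracture as time-to-event. SAP 7.1.3 can be read as excluding subjects with no readable film, but it does not say when an included stent is censored. SAP 7.9 governs changes to planned analyses, not a choice left open. Subject listings would show the individual fractures but would not settle the reported rate. The Manual of Operations, which holds the x-ray procedures, is not among the documents. A dating rule there cannot be excluded, but the SAP refers to none.

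**Conclusion.** The point holds as a gap in the analysis specification, worth fixing because the fix is nearly free. The text establishes that fracture is ascertained on windowed, pre-re-intervention and unscheduled films, is read at exact days from a survival curve, and has neither a dating rule nor film-based censoring.

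The size is conditional. Under film dating and uniform film days, 3.1% found would read on average 1.6% or 2.2% at 1 year, depending on censoring. Under nominal-visit dating it reads 3.1%. These figures rest on an assumed film-day distribution, one stent per subject and full in-window compliance. They show how far the unstated choice can move the result and do not predict the study's rate. The effect is concentrated at 1 year and can vanish by 3 years if few new fractures appear. The endpoint stays descriptive, and the primary test and the sample size are untouched.

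**What to change.** In SAP 7.7:

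- **Main result.** At 1, 2 and 3 years, report the fracture proportion among stents with a readable film in that visit window (or a fracture found earlier), with an exact interval. At one stent per subject, 3/97 would be reported as 3.1% (0.6% to 8.8%). This matches the quantity used for sizing.
- **Kaplan-Meier plot, event dates.** Assign in-window films to day 365, 730 or 1095. Date fractures found on out-of-window or pre-re-intervention films to the film.
- **Kaplan-Meier plot, censoring.** Censor a fracture-free stent at its last readable film (the nominal day if that film is in window), not at last contact. State that this replaces the SAP 7.4 rule for this endpoint.
- **Sensitivity analysis.** An interval-censored (Turnbull) estimate may be added, but not as an alternative to the main result.

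The cost is a few sentences and a little programming. The reported 1-year fracture rate will probably be somewhat higher than under film dating.
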